### 13.5 Analysis of Primary Endpoints

Cumulative incidence of VTE at day 17 (in arm A) and major hemorrhage endpoints at day 14 (both arms) will be calculated along with their 90% exact binomial confidence intervals.

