**5.3 Off treatment procedures (unblinding)**

Following the completion of the day 14 assessment, study staff will contact a clinical research pharmacist at BIDMC. Criteria for off treatment will be reviewed and then the study staff will be informed as to whether the participant was previously assigned to Arm A (standard enoxaparin) versus Arm B (weight-based enoxaparin). For participants randomized to Arm A, a bilateral ultrasound will be scheduled (see study calendar) to evaluate for asymptomatic deep vein thrombosis.

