9.2.1.3 Site Performing Correlative Studies: BIDMC

## 10. STUDY CALENDAR

Baseline evaluations are to be conducted within 48 hours prior to start of protocol therapy.

Event/Procedure	Screening/ Pre-treatment	Day 1	Days 2-6 a	Day 7 a,c	Days 8-13 a	Day 14	Day 17
Day Range	-2 to 0			± 1 day		-4, +7 days	± 5 days
Eligibility Assessments	X						
Informed Consent	X						
Inclusion/Exclusion Criteria	X						
Medical History	X						
ECOG Performance Status Score	X						
Concomitant medication review	X			X		X	
Randomization	X						
Administer enoxaparin		X	X	X	X	X	
Clinical Assessments							
Physical examination including vital signs, and height	X						
Clinical Prediction Score data collection	X						
Weight	X			X			
Assessment of signs and symptoms of VTE and bleeding	X			X		X	
Laboratory Tests							
Plasma storage for correlative studies	X						
Complete blood count	X d	X		X			
PT/PTT	X						
Creatinine	X	X		X			
AST/ALT	X						
Imaging							
Bilateral lower extremity ultrasound							X b

a: Study subjects will only remain on treatment while hospitalized or until day 14, whichever comes first.

b: Arm A ONLY (standard dose enoxaparin).

c: Day 7 study visit not mandatory if participant is no longer hospitalized.

d: Also record CBC from initial admission

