## 11. MEASUREMENT OF EFFECT

### Venous Thromboembolism (VTE)

Cumulative incidence of venous thromboembolic events is the primary endpoint for Arm A and a secondary endpoint for Arm B. ***The composite endpoint includes objectively confirmed proximal or distal lower extremity DVT, subsegmental or larger pulmonary embolism; or fatal PE diagnosed by autopsy.*** All other venous or arterial events will be recorded and analyzed as secondary endpoints (including central line associated DVT).

Participants presenting with symptoms compatible with DVT and/or PE will undergo radiographic imaging with compression ultrasound, VQ lung scan, or spiral CT. Confirmed episodes of VTE will be managed by the treating physician per standard of practice.

Presence of any of the following will be considered diagnostic for a VTE:

- New non-compressibility of lower extremity deep venous segments by compression ultrasound.
- Intraluminal defects in two or more views on pulmonary angiography
- Sudden contrast cut-off of one or more vessels greater than 2.5 mm in diameter on a pulmonary angiogram
- A high probability VQ lung scan showing one or more segmental perfusion defects with corresponding normal ventilation (mismatch defect)
- Abnormal spiral CT showing thrombus in pulmonary vessels (subsegmental or larger)

Those VTE that do not qualify for the primary endpoint such as a central line-associated thrombus will be recorded and analyzed as secondary endpoints.

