## 13.6 Analysis of Exploratory Objectives

13.6.1 Efficacy analysis: Although the study is not formally powered to determine efficacy, we will perform a secondary analysis to preliminarily compare the cumulative incidence of symptomatic VTE (data collected prior to unblinding) for the standard dose(Arm A) versus intermediate dose enoxaparin (Arm B). Accordingly, assuming a VTE event rate of 25% which is towards the upper end of the binomial confidence interval in the standard enoxaparin arm compared with a 0% event rate in the intermediate dose enoxaparin arm, the power of the study is 0.74 with a one-sided  $\alpha$  of 0.05. The cumulative incidence rate of VTE at day 17 will be estimated using the competing risk method, where VTE is the primary event and death is considered the competing event.[31]

13.6.2 Prediction models: For each of the three scoring systems (Padua, Khorana, IMPROVE), we plan to assess the 2 by 2 contingency table distributions while changing the score cut-offs (such as a Padua score  $\geq 6$  or an IMPROVE scores  $\geq 5$  or a Khorana score  $\geq 3$ ) in order to evaluate whether the classification probabilities (particularly specificity and sensitivity) change based on the chosen cut-off. The goal is to see if we can determine a more stringent cut-off (compared to a Padua score  $\geq 4$ ) by considering the Padua scoring system and/or the other 2 scoring systems to further refine hospitalized cancer patients at high risk of VTE. We aim at maintaining 100% sensitivity, while improving the specificity of the refined risk model. We fully recognize that based on the limited number of patients enrolled that we will have limited power to determine definitively whether the additional risk models can reliably improve specificity without impacting sensitivity. Therefore, we do not plan on utilizing these data to refine the inclusion/exclusion criteria for the planned phase III trial, but rather will confirm the findings within the phase III trial through stratification at time of randomization.

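### The Arm A primary VTE endpoint runs to day 17 and includes pulmonary embolism, but the last scheduled symptom check is at day 14 and the day 17 leg ultrasound cannot show a PE

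*Combined protocol and SAP*

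**What the plan says.** Section 13.5 sets the horizons of the primary analysis: "Cumulative incidence of VTE at day 17 (in arm A) and major hemorrhage endpoints at day 14 (both arms) will be calculated", with 90% exact binomial intervals. Section 11 defines the VTE composite as "objectively confirmed proximal or distal lower extremity DVT, subsegmental or larger pulmonary embolism; or fatal PE diagnosed by autopsy". Section 13.2 plans 25 participants in Arm A and works through a day 17 incidence of 12%.

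In the study calendar (section 10), the row "Assessment of signs and symptoms of VTE and bleeding" is marked at screening, day 7 and day 14. The day 17 column holds one mark, "Bilateral lower extremity ultrasound", for Arm A only. Section 5.3 gives its purpose: after the day 14 assessment and unblinding, "a bilateral ultrasound will be scheduled (see study calendar) to evaluate for asymptomatic deep vein thrombosis". The day 14 visit may fall between day 10 and day 21, and section 5.2.3 allows its symptom check by phone. The ultrasound may fall between day 12 and day 22.

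Section 13.6.1 adds a competing-risk estimate of VTE at day 17, "where VTE is the primary event and death is considered the competing event". No visit in the calendar lists vital status as an item.

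**The concern.** The other two endpoints of this kind match their assessments. Major hemorrhage is read at day 14, and so is the exploratory comparison of symptomatic VTE (section 1.3); both have a symptom check at that visit. Only the Arm A primary VTE endpoint extends past the last scheduled question about symptoms.

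A leg ultrasound finds DVT. It says nothing about a PE that occurred since the day 14 contact. Treatment ends at discharge or day 14, so many participants may be at home in that interval, and a PE could be treated at another hospital. Every participant who received one dose is assessed for the primary endpoint (section 13.7.2), and the interval is a plain binomial. Someone with an unrecorded PE and a clear scan therefore stays in the denominator as a non-event.

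For PE this error can only lower the rate. The estimate is the one that section 13.2 intends for sizing the phase III trial.

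**Working it through.** **1. The plan's own figure.** Inputs from section 13.2: n = 25 in Arm A and 12%, which is 3/25. The exact (Clopper-Pearson) 90% limits are the 5% quantile of Beta(x, n − x + 1) and the 95% quantile of Beta(x + 1, n − x). For x = 3 these are 3.35% and 28.17%. The plan states 3.3 to 28.2%, so the figure is reproduced to within 0.1 point.

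**2. Routes by which a non-fatal PE after the day 14 check could be recorded.**
- Section 11: imaging for participants who present with symptoms. No day limit is given, but nobody is scheduled to ask after the day 14 check.
- Section 5.6: PE ends protocol therapy, with a CRF entry. This does not help once therapy has already ended.
- Section 7.7: routine recording is limited to attributable events.
- Section 7.4.1: SAE reports to the Overall PI cover events attributed to heparin.
- Section 7.4.3: grade 2 and 3 events judged unrelated or unlikely need no expedited report. An unexpected grade 4 event does, but a footnote exempts events due to the malignancy or its treatment.

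None of these guarantees that a PE judged unrelated to enoxaparin reaches the database.

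**3. Length of the gap and expected number of PEs in it.** The documents give neither the timing of VTE nor the share that is PE. Assumptions: 12% VTE by day 17 (0.12 × 25 = 3 events), spread evenly over 17 days, with PE making up 20 to 50% of VTE. Expected PEs in a gap of g days = 3 × (g/17) × PE share.

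| Day 14 check done on | Days to day 17 with no check | Expected VTE | Expected PEs | If all missed, shift in rate |
|---|---|---|---|---|
| day 10 (earliest) | 7 | 3 × 7/17 = 1.24 | 0.25 to 0.62 | 1.0 to 2.5 points |
| day 14 (nominal) | 3 | 3 × 3/17 = 0.53 | 0.11 to 0.26 | 0.4 to 1.1 points |
| days 18 to 21 | 0 | 0 | 0 | 0 |

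The shift is expected PEs divided by 25. These are upper figures, because some symptomatic PEs will be imaged and reported, and a participant whose scan also shows a DVT still counts as an event.

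**4. Effect of a single missed PE.** 1/25 = 4 percentage points. If 3 events are recorded:
- none missed: 3/25 = 12%, 90% CI 3.4 to 28.2%
- one missed, true count 4/25 = 16%, 90% CI 5.7 to 33.0%
- two missed, true count 5/25 = 20%, 90% CI 8.2 to 37.5%

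**The case against.** The strongest reply is that event-driven capture already exists. Symptomatic participants are imaged whatever the day, section 5.7 follows Arm A to the day 17 scan, and section 11 sends other imaging that shows new thrombosis to adjudication. Staff must also contact Arm A participants to arrange the scan. The expected loss is about 1 point or less on nominal days, against an interval about 25 points wide. All of this stands and limits the size of the point. It does not close the gap, since every route depends on the site happening to learn of the event.

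Some stronger readings are tempting but not supported:
- **Two of the three components go unobserved.** A reader might infer this from the calendar. But fatal PE counts only if proven at autopsy, so it surfaces through a death and not through a symptom question. The gap concerns non-fatal PE.
- **Vital status in Arm A is known only from scan attendance.** Section 5.8 requires the reason and date when a participant leaves the study through death, and sections 7.4.2 and 7.4.3 make grade 5 events reportable whatever the attribution. An unrecorded death without VTE, carried as event-free to day 17, would in any case leave the cumulative incidence unchanged; early censoring would raise it.
- **Arm B needs the same contact.** The primary VTE analysis is in Arm A only, and the between-arm comparison uses symptomatic VTE collected before unblinding. The day 17 sentence in 13.6.1 names no arm, so no stated analysis clearly needs Arm B contact at day 17.
- **The unchecked period is routinely long.** Seven days requires the earliest permitted day 14 check. The same window also allows a check late enough to leave no gap.

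**Conclusion.** The point holds for non-fatal PE in Arm A. Between the day 14 check and day 17, one component of the primary composite has no scheduled assessment, and a missed case biases the Arm A rate downward. It is a gap in scheduled ascertainment and does not mean that nothing would be captured.

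The expected effect is small: about 0.1 to 0.3 PEs on nominal days, or 0.4 to 1.1 points if all were missed. This rests on an even spread of a 12% rate and on PE being 20 to 50% of VTE; neither the timing nor the share is given in the documents. The number actually missed may well be zero. The change is still worth making because the planning case has only three events, one missed PE moves the estimate by 4 points, and the remedy costs almost nothing.

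**What to change.** In the study calendar, mark the row "Assessment of signs and symptoms of VTE and bleeding" in the day 17 column for Arm A. Do it when the participant attends for the ultrasound, or by phone if the scan is missed. At that contact:
- ask about any imaging or hospital admission elsewhere since the day 14 check;
- confirm vital status;
- send any positive imaging to the VTE adjudication already set up in section 11.

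The CRF needs a matching page. The cost is a few minutes at an existing visit and an occasional phone call. Sample size, analysis method and treatment rules are unaffected, and no extra Arm B contact is needed for the primary analysis.

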## 13.6 Analysis of Exploratory Objectives

13.6.1 Efficacy analysis: Although the study is not formally powered to determine efficacy, we will perform a secondary analysis to preliminarily compare the cumulative incidence of symptomatic VTE (data collected prior to unblinding) for the standard dose(Arm A) versus intermediate dose enoxaparin (Arm B). Accordingly, assuming a VTE event rate of 25% which is towards the upper end of the binomial confidence interval in the standard enoxaparin arm compared with a 0% event rate in the intermediate dose enoxaparin arm, the power of the study is 0.74 with a one-sided  $\alpha$  of 0.05. The cumulative incidence rate of VTE at day 17 will be estimated using the competing risk method, where VTE is the primary event and death is considered the competing event.[31]

13.6.2 Prediction models: For each of the three scoring systems (Padua, Khorana, IMPROVE), we plan to assess the 2 by 2 contingency table distributions while changing the score cut-offs (such as a Padua score  $\geq 6$  or an IMPROVE scores  $\geq 5$  or a Khorana score  $\geq 3$ ) in order to evaluate whether the classification probabilities (particularly specificity and sensitivity) change based on the chosen cut-off. The goal is to see if we can determine a more stringent cut-off (compared to a Padua score  $\geq 4$ ) by considering the Padua scoring system and/or the other 2 scoring systems to further refine hospitalized cancer patients at high risk of VTE. We aim at maintaining 100% sensitivity, while improving the specificity of the refined risk model. We fully recognize that based on the limited number of patients enrolled that we will have limited power to determine definitively whether the additional risk models can reliably improve specificity without impacting sensitivity. Therefore, we do not plan on utilizing these data to refine the inclusion/exclusion criteria for the planned phase III trial, but rather will confirm the findings within the phase III trial through stratification at time of randomization.

13.6.3 Biomarkers: The primary analysis of each of the biomarkers is to identify whether any of the pre-defined cutoff values are sensitive for VTE in the high risk cancer patients randomized to fixed-dose enoxaparin. Biomarkers such as tissue factor bearing microparticles and D-dimer have previously demonstrated low positive predictive values but high negative predictive values in cancer cohorts.[26, 28, 29] The combination of high tissue factor bearing microparticles ( $>3.5 \times 10^4$  microparticles/ $\mu$ l, the top tercile of tissue factor-bearing microparticle concentrations from the reference specimens) and elevated D-dimer further improved the sensitivity and specificity of the individual assays.[26] We will evaluate whether any of the individual biomarkers or combination of biomarkers are sensitive to identify all VTE diagnosed in the high risk cancer patients randomized to fixed-dose enoxaparin. We plan to assess the 2 by 2 contingency table distributions using the pre-defined cut-off values in order to evaluate the classification probabilities (particularly specificity and sensitivity) based on the chosen cut-off. The top tercile of tissue factor-bearing microparticle concentrations and D-dimer or the age-adjusted D-dimer cut-off of the study cohorts will be also considered to evaluate the classification probabilities of the classification model. Fine and Gray univariate regression models will be used to assess the impact of each biomarker classification on the risk of developing VTE. In addition, using regression models we aim at assessing whether there is an association between the scores in the scoring systems and the biomarkers. As this is the initial exploratory evaluation of PSGL-1+ microparticles and thrombosis, additional validation in the phase III trial will be required.

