### 1.3 Exploratory Objectives

- Compare rates of symptomatic VTE between enoxaparin arms at day 14
- Evaluate the performance of clinical scoring models (ie. Padua, IMPROVE, and Khorana Score) in predicting thrombotic risk in hospitalized cancer patients
- Assess the prognostic value of biomarkers (e.g. D-dimer and microparticles) to predict thrombosis in hospitalized cancer patients

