**9. BIOMARKER, CORRELATIVE, AND SPECIAL STUDIES**

## **9.1 Biomarker Studies**

We previously demonstrated the predictive value of circulating tissue factor bearing microparticles in cancer outpatients. We will evaluate if the number of tissue factor bearing microparticles upon hospitalization predicts thrombotic risk. Microparticles will be isolated from plasma by differential centrifugation. We modified an impedance-based flow cytometry system (Beckman Coulter SC Quanta) in order to address the shortcomings of standard light scatter based flow cytometry in the measurement of small ( $<1\text{ }\mu\text{m}$ ) particles.[21] Using this methodology we observed a significant correlation between elevation in tissue factor bearing microparticles and the development of cancer-associated thrombosis.[21, 26]

Based on animal models suggesting that tumor derived tissue factor bearing microparticles accumulate at the site of a developing thrombus through the binding of PSGL-1 with P-selectin, we will evaluate whether subpopulations of TF-bearing microparticles are associated with thrombosis in hospitalized cancer patients. By flow cytometry, we will determine the percentage of TF-bearing microparticles co-expressing the PSGL-1, MUC1, and/or CD14 antigens.

D-dimer is a degradation product of cross-linked fibrin and is the most widely utilized sensitive biomarker to exclude venous thromboembolic events.[27, 28] Utility of D-dimer alone to predict thrombosis in cancer patients is limited due to poor specificity especially using standard cut-offs.[29] D-dimer will be measured by using a commercially available immunoassay (Roche Diagnostics). We will analyze the association between thrombosis and elevated D-dimer values based on standard cutoff of  $>500\text{ng/L}$ , 75th percentile based on measurements using stored plasma from cancer patients[21, 29] or age adjusted-cutoff which was recently demonstrated to improve assay specificity in a large cohort of patients (including 429 patients with active malignancy).[28] In order not to confound study outcomes, D-Dimer measurements will be performed centrally at BIDMC after the completion of the trial and will not be recorded in the participant's medical record.

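### Section 13.6.3 relates D-dimer and microparticles to VTE only as high/low classes; add an analysis of the measured values beside the class analyses

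*Combined protocol and SAP*

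**What the plan says.** Section 1.3 lists among its exploratory objectives: "Assess the prognostic value of biomarkers (e.g. D-dimer and microparticles) to predict thrombosis in hospitalized cancer patients". Section 9.1 puts the microparticle question in terms of a count: "We will evaluate if the number of tissue factor bearing microparticles upon hospitalization predicts thrombotic risk".

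Section 13.6.3 then turns to classes:

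- Its declared main question is about cut-offs: "The primary analysis of each of the biomarkers is to identify whether any of the pre-defined cutoff values are sensitive for VTE", in the patients on fixed-dose enoxaparin.
- The tables follow from that: "We plan to assess the 2 by 2 contingency table distributions using the pre-defined cut-off values in order to evaluate the classification probabilities".
- The one association model for VTE also uses classes: "Fine and Gray univariate regression models will be used to assess the impact of each biomarker classification on the risk of developing VTE".

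The microparticle threshold is "the top tercile of tissue factor-bearing microparticle concentrations from the reference specimens". For D-dimer, section 9.1 names a standard cut-off, a 75th "percentile based on measurements using stored plasma from cancer patients", and an age-adjusted cut-off. Section 13.6.3 also mentions top terciles of the study cohort itself. Its remaining regression relates the biomarkers to the clinical risk scores, not to VTE. No test, alpha or power is stated for any biomarker analysis.

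**The concern.** Both markers are measured on a continuous scale. A high/low class treats a patient just above the cut like one far above it, and separates two patients who lie close together on either side. That suits the evaluation of a decision rule. It is a coarse way to ask whether a marker carries prognostic information, which is what sections 1.3 and 9.1 ask.

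With about 3 events, one VTE just below the threshold can remove the signal. A marker worth taking to phase III could then look uninformative, and the report would hold no analysis of the measured values to set against that.

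**Working it through.** **1. Expected events.** Section 13.2 gives 25 patients in Arm A and 12% VTE: 0.12 × 25 = 3. The exact 90% interval for 3/25 is 3.35% to 28.17%, which agrees with the plan's 3.3 to 28.2% apart from rounding. The probability of 0 or 1 event is 0.88^25 + 25 × 0.12 × 0.88^24 = 0.18.

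**2. What a class can show with 3 VTE in 25.** There are C(25,3) = 2300 equally likely placements under no association. Suppose 8 of 25 are high (about a tercile).

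- All 3 VTE high: C(8,3)/2300 = 56/2300, p = 0.024.
- At least 2 of 3 high: (56 + 28 × 17)/2300 = 532/2300, p = 0.23.
- Ranks, for comparison: if the three VTE rank 1st, 4th and 9th from the top, one lies just below the cut. The class result is then p = 0.23. The rank sum is 14, and 41 of the 2300 triples have a sum of 14 or less, so p = 0.018.
- Section 9.1 says the use of D-dimer alone "is limited due to poor specificity especially using standard cut-offs". If 19 of 25 were high (an assumption), all 3 VTE high gives C(19,3)/2300 = 969/2300, p = 0.42, so an exact class test could not reach 0.05.

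**3. Large-sample information kept.** For a normal marker with a log-linear effect, cut so that a share q is high, the share kept is φ(c)²/[q(1−q)]. This is 59% at the top tercile, 54% at the top quarter and 34% when 10% or 90% are high. The expression is a squared correlation between value and class. It is therefore also the share kept by the continuous analysis when risk truly steps at the cut.

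**4. Power by simulation.** Settings: n = 25, 12% VTE overall, normal log-biomarker, one-sided 0.05, 15,000 trials per scenario. The one-sided level is borrowed from the arm comparison in 13.6.1. The slope is set so that the top tercile versus the rest has an odds ratio taken from rates in section 2.4:

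- 27% vs 7.2%: (0.27/0.73)/(0.072/0.928) = 4.8.
- 43% vs 4.2%: (0.43/0.57)/(0.042/0.958) = 17.2.

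| Log-linear truth, top tercile | OR 4.8: class vs value | OR 17.2: class vs value |
|---|---|---|
| Score tests | 0.353 vs 0.417 | 0.660 vs 0.748 |
| Exact tests, size-matched | 0.291 vs 0.395 | 0.555 vs 0.736 |

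The score tests lose 6 and 9 points, and the size-matched exact tests 10 and 18. At a 75th-percentile cut the score tests lose about 3 to 5. Across repeated runs the score-test loss was about 2 to 9.

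**5. Least favourable truth: a step at the cut.** Size-matched exact tests, class vs value: 0.290 vs 0.261 and 0.554 vs 0.504, so the value loses 3 and 5 points. On score tests the penalty is larger: a check with the same settings gave about 0.37 vs 0.25 and 0.67 vs 0.48. Part of that gap is size, since the class score test rejects slightly too often under no effect.

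**6. Power in absolute terms.** In a separate proportional-hazards simulation (25 patients, 3 events, two-sided 0.05), the continuous analysis had power of only about 0.10 to 0.40 for hazard ratios of 1.5 to 3 per SD.

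**The case against.** The strongest reply is that cut-offs are the declared question. Section 13.6.3 makes the sensitivity of pre-defined thresholds the primary biomarker analysis, section 9.1 specifies D-dimer associations at named thresholds, and modelling the same classes is coherent. That stands, and it rules out dropping the class analyses.

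A reader might infer that the continuous analysis should replace them. The documents do not support this. A rank-sum test ignores death as a competing event, which 13.6.1 takes into account. A single D-dimer value drops the age adjustment. One continuous covariate cannot represent the planned marker combination.

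A reader might also infer a loss of up to 37 points, from 0.34 for Fisher's exact test on the class against 0.71 for an exact rank test on the values (OR 17.2). That does not hold as a cost of this plan:

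- Section 13.6.3 specifies no Fisher test. With 25 patients and a top-tercile cut, that test's true one-sided size is about 0.010, so much of the gap is conservatism.
- The 43% vs 4.2% contrast in section 2.4 compares patients with both markers raised against all others. Forced onto one marker, it implies an odds ratio of about 7.9 per SD.
- The 27% is the rate in high-microparticle patients randomised to observation. Everyone in Arm A receives enoxaparin, and section 2.4 gives 5% for high-microparticle patients on it.

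The last two points also apply to the smaller figures in the working, which is why they are only conditional. It is true as well that 3 events limit any coding of the marker.

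**Conclusion.** The gap is real but modest: nothing in 13.6.3 relates a measured biomarker value to VTE, although sections 1.3 and 9.1 pose a prognostic question. Under log-linear risk, the class-based approach loses about 2 to 9 points of power on score tests, the closer analogue of the planned regression, and about 10 to 18 on size-matched exact tests. If risk steps at the threshold the advantage reverses: 3 to 5 points on size-matched exact tests, and more on score tests.

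These figures rest on an assumed normal log-biomarker, a one-sided 0.05 level that the plan does not set for biomarkers, and effect sizes borrowed from a different setting. None is a property of the plan itself. The number of events is the larger limit. Since neither shape of effect can be presumed, the case is for reporting both analyses. This is an optional improvement to an exploratory objective and does not affect the primary endpoints.

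**What to change.** Keep the 2 by 2 tables at the pre-defined cut-offs and the class-based Fine and Gray model. Add to 13.6.3, for D-dimer and for TF-bearing microparticle concentration:

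- a univariate Fine and Gray model with the log-transformed value as one continuous covariate and death as the competing event, reported as a hazard ratio per doubling with its confidence interval;
- in Arm A, a descriptive AUC with confidence interval and an exact rank-sum test of the values in patients with versus without VTE.

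State whether the Fine and Gray models use Arm A alone or both arms; the present sentence does not say.

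The cost is SAP wording and one more exploratory analysis per marker, on the same assays and patients. A hazard ratio per doubling is less directly clinical than high versus low, which the retained tables cover. The continuous model has less power than the class model if risk steps at the cut-off, which is why both are reported.
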